- d. Site staff is to administer the C-SSRS, SBQ-R and PHQ-8 to all subjects at screening and score immediately. Subjects who have recent or active suicidal ideation or behavior or clinically significant depression will be excluded from the study or discontinued from the study per [Section 4.2](#), [Section 7.5.1](#), [Section 7.5.2](#) and [Section 7.5.3](#). Subjects meeting exclusionary results on the C-SSRS, SBQ-R and PHQ-8 should be excluded from participation; it is recommended the subject's primary care physician (PCP) should be informed, and the subject referred to a mental health professional, either by the PCP or the investigator according to their usual practice. Post-screening, if there are "yes" answers on items 4, 5 or on any behavioral question of the Since Last Visit C-SSRS a risk assessment by a qualified mental health professional (MHP) should be done to determine whether it is safe for the subject to continue to participate in the trial.
- e. Atopic Dermatitis Disease History includes collection of details of AD: AD diagnosis and duration, the use of topical treatments, systemic treatments and other treatments for AD.
- f. Complete physical examinations must be performed by the investigator, sub investigator or a qualified health professional per local guidelines. Complete physical examinations consist of assessments of general appearance; skin; head, eyes, ears, nose and throat (HEENT); mouth, heart; lungs; breast (optional); abdomen; external genitalia (optional); extremities; neurologic function; and lymph nodes. Targeted physical examinations must be performed by the investigator, sub-investigator or a qualified health professional per local guidelines and should include skin, heart, lungs, and abdomen and examination of body systems where there are symptom complaints by the subject.
- g. Vital Signs include sitting blood pressure, pulse, respiratory rate, and temperature measured after at least 5 minutes of rest.
- h. Laboratory tests with abnormal results (per [Section 6.1](#) and [Section 7.6.2](#)) may be repeated once during the screening period; the last value will be used to determine eligibility.

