**Figure 1. Study Design Schematic**

Enrolled subjects initiate the 12-week, open-label run-in period to identify responders who have a positive clinical response to induction treatment with 200 mg PF-04965842 QD.

**Responder criteria** are defined as a) achieving an IGA of clear (0) or almost clear (1) (on a 5-point scale), b) a reduction from IGA baseline of  $\geq 2$  points, and c) reaching an EASI-75 response compared to baseline. Baseline is defined as the IGA score and EASI score obtained prior to dosing on Day 1. Subjects meeting all responder criteria may be eligible for randomization. Subjects who do not reach the response threshold required for randomization are declared non-responders after completion of the open label run-in period.

Non-responders are not eligible for randomization in this study but may choose to enroll into the PF-04965842 Long Term Extension (LTE) study B7451015 providing they remain eligible; otherwise, they are permanently discontinued from treatment and enter the 4-week untreated follow-up period in this study.

Responders at the end of the 12-week open-label run-in period enter the 40 week, double-blind, maintenance treatment period in which they are randomized into 1 of 3 treatment arms in a 1:1:1 ratio:

1. 100 mg PF-04965842 QD;
2. 200 mg PF-04965842 QD;
3. Placebo.

All subjects who have started wash-out of AD treatment in the screening period will be allowed to enter the run-in and treatment periods providing all inclusion criteria and none of the exclusion criteria are met. Randomization is stratified by age category, ie, <18 years and  $\geq$ 18 years. Eligible subjects must have a documented history of inadequate response with topical AD medications or have required systemic therapies for control of their disease.

Medicated topical and/or systemic standard of care therapies are not allowed during the open-label run-in and blinded treatment periods. Medicated topical therapy is defined as a topical product that contains an active pharmaceutical ingredient indicated for the treatment of AD (irrespective of whether it is an over-the-counter [OTC] or prescription only product).

Following completion of the 40-weeks of blinded treatment, all subjects are assessed for eligibility to enter the PF-04965842 LTE study B7451015. If a subject discontinues prematurely or is not eligible/willing to participate in B7451015, then the subject enters the 4-week untreated follow-up period.

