## 4.2. Exclusion Criteria

Subjects with any of the following characteristics/conditions will not be included in the study:

1. Other acute or chronic medical or psychiatric condition including recent (within the past year) or active suicidal ideation or behavior or laboratory abnormality that may increase the risk associated with study participation or investigational product administration or may interfere with the interpretation of study results and, in the judgment of the investigator, would make the subject inappropriate for entry into this study.
2. Any psychiatric condition including recent or active suicidal ideation or behavior that meets any of the following criteria:
  - Suicidal ideation associated with actual intent and a method or plan in the past year: “Yes” answers on items 4 or 5 of the Columbia suicide severity rating scale (C-SSRS) ([Appendix 15](#));
  - Previous history of suicidal behaviors in the past 5 years: “Yes” answer (for events that occurred in the past 5 years) to any of the suicidal behavior items of the C-SSRS;
  - Any lifetime history of serious or recurrent suicidal behavior;
  - Suicidal behaviors questionnaire – revised (SBQ-R) total score  $\geq 8$  ([Appendix 17](#));
  - Clinically significant depression: patient health questionnaire – 8 items (PHQ-8) total score  $\geq 15$  ([Appendix 18](#));
  - The presence of any current major psychiatric disorder that is not explicitly permitted in the inclusion/exclusion criteria;
  - In the opinion of the investigator or Pfizer (or designee) exclusion is required.
3. A current or past medical history of conditions associated with thrombocytopenia, coagulopathy or platelet dysfunction.
4. Receiving anti-coagulants or medications known to cause thrombocytopenia (unless considered safe to stop and washout for the duration of the study).
5. Currently have active forms of other inflammatory skin diseases, ie, not AD or have evidence of skin conditions (eg, psoriasis, seborrheic dermatitis, Lupus) at the time of Day 1 that would interfere with evaluation of atopic dermatitis or response to treatment.

6. Vaccinated or exposed to a live or attenuated vaccine within the 6 weeks prior to the first dose of investigational product, or is expected to be vaccinated or to have household exposure to these vaccines during treatment or during the 6 weeks following discontinuation of investigational product.

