#### 6.2.6. Visit 7, Day 57/Week 8 ( $\pm 3$ days)

- Administer and score the Since Last Visit C-SSRS. For subjects meeting any of the criteria specified in [Section 7.5.1](#) a risk assessment by a qualified MHP should be done to determine whether it is safe for the subject to continue to participate in the trial;
- Administer PROs including: PtGA, DLQI (or CDLQI), POEM, HADS and EQ-5D-5L (or EQ-5D-Y in select countries);
- Adolescents 12-17 years of age will complete the CDLQI instead of the DLQI and the EQ-5D-Y in select countries instead of the EQ-5D-5L;
- Review PSAAD daily completion (in selected countries) and pruritis NRS completion for this visit in the eDiary;
- Review any changes in the subject's concomitant medications and treatments information;
- Obtain vital signs including pulse rate, blood pressure, respiratory rate and oral or tympanic temperature (after at least 5 minutes of rest);
- Perform a single 12-lead ECG;
- Conduct targeted physical examination;
- Conduct clinical evaluations including IGA, SCORAD, EASI and BSA (calculated in the EASI);
- Obtain samples for laboratory testing: serum chemistry, hematology (including coagulation panel, RBC/WBC Indices, lymphocyte subsets and markers) and urinalysis;
- Urine pregnancy test (female subjects of childbearing potential including adolescents aged 12 years and older regardless of whether they have experienced menarche). A negative urine pregnancy test must be obtained prior to dosing with the investigational product;
- Assess need for contraception and adherence to applicable lifestyle requirements ([Section 4.4](#)). Establish willingness and ability to comply with lifestyle requirements going forward in the study;
- Review eDiary to assess completion;
- Perform drug accountability procedures;
- Administer investigational product to the subject;

- Dispense investigational product to the subject;
- Assess and record any Adverse Events since the last visit.

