### **6.3. Double-Blind Maintenance Treatment Period**

#### **6.3.1. Visit 8, Day 85/Week 12 ( $\pm 3$ days) Randomization into Maintenance Treatment**

- Administer and score the Since Last Visit C-SSRS. For subjects meeting any of the criteria specified in [Section 7.5.1](#) a risk assessment by a qualified MHP should be done to determine whether it is safe for the subject to continue to participate in the trial;
- Administer PROs including: PtGA, DLQI (or CDLQI), POEM, HADS, EQ-5D-5L (or EQ-5D-Y in select countries), SF-36v2, Acute and FACIT-F (or Peds-FACIT-F). SF-36v2 will be completed by adult subjects only;
- Adolescents 12-17 years of age will not complete the SF-36v2. Adolescents 12-17 years of age will complete the CDLQI instead of the DLQI, the EQ-5D-Y in select countries instead of the EQ-5D-5L and Peds-FACIT-F instead of the FACIT-F;
- Review PSAAD daily completion (in selected countries) and pruritus NRS completion for this visit in the eDiary;
- Obtain weight for all subjects and height for adolescents only (12 to <18 years old);
- Obtain vital signs including pulse rate, blood pressure, respiratory rate and oral or tympanic temperature (after at least 5 minutes of rest);
- Perform a single 12-lead electrocardiogram (ECG);
- Conduct complete physical examination;
- Conduct clinical evaluations including IGA, SCORAD, EASI and BSA (calculated in the EASI);
- Obtain fasting samples for laboratory testing: serum chemistry, hematology (including coagulation panel, RBC/WBC Indices, lymphocyte subsets and markers), lipid profile, and urinalysis;
-  
- For China and Taiwan only: For subjects who had HBV DNA testing at Screening, collect blood sample for repeat HBV DNA testing;

- Urine pregnancy test (female subjects of childbearing potential including adolescents aged 12 years and older regardless of whether they have experienced menarche). A negative urine pregnancy test must be obtained prior to dosing with the investigational product;
- Determine if the subject meets all of the **responder criteria for randomization**:
  - a. IGA of clear (0) or almost clear (1);
  - b. A reduction in IGA from baseline (Day 1) of 2 points or more, and
  - c. Reaching an EASI-75 response compared to baseline;
- Review of Inclusion/Exclusion Criteria;
- Randomize subject if all responder and inclusion criteria are met, and none of the exclusion criteria are met;

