##### **7.5.1. Columbia Suicide Severity Rating Scale (C-SSRS)**

The Columbia Suicide Severity Rating Scale is a validated tool for investigative staff to use to evaluate suicidal ideation and behavior ([Appendix 15](#)). At the screening visit, if there are "yes" answers on items 4 or 5 in the past year or on any question in the suicidal behavior section of the C-SSRS in the past 5 years, the subject will not be included in the study. Trained site staff will administer the C-SSRS to all subjects at screening and score immediately to assess the subject's eligibility based on the answers.

At post-baseline visits, if there are "yes" answers on items 4, 5 or on any behavioral question of the Since Last Visit C-SSRS ([Appendix 16](#)), a risk assessment by a qualified MHP should be done to determine whether it is safe for the subject to continue to participate in the trial.

Subjects who have recurrent suicidal ideation and behavior (SIB) during a clinical trial should be discontinued from the study and treated appropriately. If a study subject endorses a 4 or 5 on the ideation subscale or any behavioral item of the C-SSRS on more than 2 occasions and is confirmed to have active SIB on both occasions by a risk assessment conducted by a qualified MHP, then the subject should be discontinued from the study and treated appropriately. These subjects should be discussed with the Pfizer Medical Monitor.

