### **Discontinuation Criteria**

Subjects must be permanently discontinued from treatment if they meet any of the following criteria at any point in the study:

- Marked prolongation of the Fridericia-corrected QT (QTcF) interval to  $>500$  ms or  $>60$  ms change from screening ECG.
- Serious infection (see definition for Serious Adverse Events in [Section 8.2.3](#)).

- Any bleeding event thought to be associated with a platelet count reduction per the judgement of the investigator (or, if necessary/desired, following discussion with sponsor).
- Other adverse event, per judgment of the investigator, requiring discontinuation from treatment (or, if necessary/desired, following discussion with sponsor).
- Any adverse event or laboratory abnormality, that per the investigator's judgement requires temporary interruption to dosing of investigational product for >28 days.

NOTE: any initial lab value below must be retested, within 48 hours.

- Two sequential platelet counts  $<50,000/\text{mm}^3$ . If the subject has a platelet count  $<25,000/\text{mm}^3$ , investigational product should be temporarily withheld pending the confirmatory retest.
- Two sequential neutrophil counts  $<500/\text{mm}^3$ .
- Two sequential lymphocyte counts  $<500/\text{mm}^3$ .
- Two sequential hemoglobin assessments  $<8.0 \text{ g/dL}$  or  $\leq 30\%$  from baseline value.

Any of the following:

- Two sequential AST or ALT elevations  $>3$  times the upper limit of normal with at least one total bilirubin value  $>2$  times the upper limit of normal.
- Two sequential AST or ALT elevations  $>3$  times the upper limit of normal with an abnormal INR.
- Two sequential AST or ALT elevations  $>3$  times the upper limit of normal accompanied by symptoms consistent with hepatic injury.
- Two sequential AST or ALT elevations  $>5$  times the upper limit of normal, regardless of total bilirubin or accompanying symptoms.

**Note: Any of the above findings should prompt review of “The Potential Cases of Drug-Induced Liver Injury”, [Section 8.4.1](#) for which additional investigations must be conducted.**

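### Section 7.5.1 gives two different counts for its suicidality stop rule, at least three occasions and two, and nothing else in the documents says which applies to subjects already randomized or in rescue

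*Protocol*

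**What the plan says.** Section 7.5.1 handles a post-baseline positive answer (item 4, item 5 or any behavior item on the Since Last Visit form) in three steps.

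- Each positive calls for a risk assessment by a qualified MHP, who judges whether the subject can safely continue.
- A general sentence follows: "Subjects who have recurrent suicidal ideation and behavior (SIB) during a clinical trial should be discontinued from the study and treated appropriately". It gives no number.
- The counted rule comes next. The subject is to be discontinued after endorsing such an item "on more than 2 occasions and is confirmed to have active SIB on both occasions by a risk assessment conducted by a qualified MHP".

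Other places bear on stopping but give no count. Footnote d of the run-in and blinded Schedule of Activities says that subjects with recent or active "suicidal ideation or behavior or clinically significant depression will be excluded from the study or discontinued from the study", and then points back to Sections 4.2 and 7.5.1 to 7.5.3. Footnote t of the rescue schedule repeats only the MHP step. Appendix 4 opens its list with "Subjects must be permanently discontinued from treatment if they meet any of the following criteria at any point in the study", but no item in that list concerns suicidality.

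**The concern.** The counted rule is the only numeric suicidality stop rule in the protocol. The MHP assessment is a case-by-case judgment. A counted rule exists to take that judgment out of play once active SIB has been confirmed repeatedly, and it can do so only if it has one count. As written, a site that reads the trigger and a site that reads the confirmation clause will act differently on the same subject. One stops after the second confirmed episode, and the other sees no counted requirement until a third. The trial enrolls from age 12 and has about 218 sites, so uneven application is a fair concern even if the event is rare.

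**Working it through.** No power or error-rate calculation is involved. The check compares the two counts with the C-SSRS schedule.

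**Counts.** More than 2 means 3 or more. Both means exactly 2. A reader could try to reconcile them as three endorsements of which two are confirmed, but with three or more occasions the word both has nothing to refer to. Even on that reading the earliest counted stop is the third endorsement, so the dates are the same as for a count of three.

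**Schedule.** After the first dose, the C-SSRS is due at Weeks 8 (Day 57), 12 (Day 85), 16 (Day 113), 28 (Day 197), 40 (Day 281) and 52 (Day 365), and at end of study. In rescue it is due at Rescue Weeks 0 (Day 1), 8 (Day 57) and 12 (Day 85), and at end of study.

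**Gap.** For two consecutive confirmed positives, gap = day of the next scheduled C-SSRS minus day of the second positive.

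| Confirmed positives | Stop if the count is 2 | Earliest stop if the count is 3 | Gap |
|---|---|---|---|
| Weeks 16 and 28 | Day 197 | Day 281 | 281 − 197 = 84 days, 12 weeks |
| Weeks 28 and 40 | Day 281 | Day 365 | 365 − 281 = 84 days, 12 weeks |
| Weeks 12 and 16 | Day 113 | Day 197 | 197 − 113 = 84 days, 12 weeks |
| Rescue Weeks 0 and 8 | Rescue Day 57 | Rescue Day 85 | 85 − 57 = 28 days, 4 weeks |

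Four remarks on the table:

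- These are nominal days. Weeks 28 and 40 each have a window of ±7 days, so the first gap can run from 84 − 14 = 70 to 84 + 14 = 98 days.
- The Weeks 12 and 16 row applies only if a subject with a positive at Week 12 was randomized at all. The Week 12 eligibility review in Section 6.3.1 should normally prevent that.
- For Weeks 28 and 40, and for Rescue Weeks 0 and 8, the third occasion is also the planned end of that treatment period. The gap is then extra time on treatment, and the later stop itself changes little. For Weeks 40 and 52, blinded treatment ends at Week 52 on either count.
- Each gap is the shortest one at scheduled visits. If no third positive occurs, a count of three never triggers.

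**Arm comparison.** Subjects and investigators are blinded in the maintenance period, and the same wording applies in all arms. The reading chosen can move the date on which a discontinued subject is censored (SAP Section 5.3.3, last date of dosing). Nothing in the documents suggests that it would do so differently by arm.

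**The case against.** The strongest reply is that this is an editorial slip with several safeguards around it, and most of that stands. Two MHP-confirmed episodes are recurrent in the ordinary sense, so the general sentence in 7.5.1 already supports stopping at the second. Every positive brings an MHP assessment. Section 6.6 lets the investigator or sponsor withdraw a subject for safety or behavioral reasons, Appendix 4 allows a stop for any adverse event by investigator judgment, and unplanned visits are permitted. It would therefore overstate the case to say that nothing requires a stop before a third occasion. The accurate statement is that no counted stop applies. These safeguards soften the ambiguity, but all of them rest on judgment and none gives the number.

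A reader might also infer that a responder confirmed at Weeks 8 and 12 could still be randomized, and so withdrawn to placebo, on the three-occasion reading. The documents do not support that. Section 6.3.1 and the Schedule repeat the eligibility review at Week 12, and the instruction is "Randomize subject if all responder and inclusion criteria are met, and none of the exclusion criteria are met". Exclusion criterion 2 covers the same items: it bars "Suicidal ideation associated with actual intent and a method or plan in the past year" (items 4 and 5) and any behavior item within 5 years. A single positive at Week 8 or 12 falls inside both windows, whichever count 7.5.1 uses. It is true that the review cannot be applied to the letter. Criterion 8 excludes prior JAK inhibitor treatment, and every subject has by then taken one for 12 weeks. Criterion 2 also cites the screening form. Even so, the natural and safer reading is that criterion 2 bars this subject. Nor do the documents link placebo assignment to suicidality.

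**Conclusion.** The rule is wrong as written. Its trigger needs at least three occasions, its confirmation clause needs two, and no other text chooses between them. The consequence is confined mainly to the blinded maintenance and rescue periods, where criterion 2 plays no part. At scheduled visits the two counts put the counted stop 12 weeks apart in the blinded period and 4 weeks apart in rescue. The clearest case is Weeks 16 and 28: both positives come after randomization, and treatment is still planned beyond the third occasion.

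These sizes assume consecutive confirmed positives, an MHP who allows the subject to continue each time, and no unplanned C-SSRS in between. The number affected is likely to be very small or zero. This is a subject-safety point with no consequence for the primary comparison. It merits correction because a stop threshold should have a single value and correcting it costs almost nothing.

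**What to change.** 1. In Section 7.5.1, make the trigger read *on 2 or more occasions* and the confirmation clause read *on at least 2 of these occasions*. This keeps the stricter count and agrees with the preceding sentence on recurrent SIB.
2. Add the same rule as one bullet in the Appendix 4 discontinuation list, so that sites find it with the other mandatory stops.

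Leave Section 6.3.1 as it is. A new sentence there allowing randomization after a positive on the strength of an MHP clearance could loosen the criterion 2 check that already applies at Week 12.

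The cost is one reworded sentence and one bullet. The C-SSRS and the MHP assessment are already required at these visits, so there is no new procedure, and the SAP does not change.

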##### **7.5.2. Suicidal Behaviors Questionnaire-Revised (SBQ-R)**

The Suicidal Behaviors Questionnaire-Revised ([Appendix 17](#)) is a patient-reported questionnaire consisting of 4 items to assess suicidal ideation, suicide attempts, threat of suicidal behavior, and likelihood of suicidal behavior. At the Screening Visit, if SBQ-R total score  $\geq 8$ , the subject will not be included in the study. Site staff will administer the SBQ-R to all subjects at screening and score immediately.

##### **7.5.3. Patient Health Questionnaire – 8 items (PHQ-8)**

The Patient Health Questionnaire – 8 items ([Appendix 18](#)) is a patient-reported questionnaire consisting of 8 items to assess the subject's depression level. At Screening Visit, if PHQ-8 total score  $\geq 15$ , the subject will not be included in the study. Site staff will administer the PHQ-8 to all subjects at screening and score immediately.

